12.6.2 Evaluable Disease

Evaluable disease is defined as at least one lesion, with no lesion that can be accurately measured in at least one dimension. Such lesions may be evaluable by nuclear medicine techniques, immunocytochemistry techniques, tumor markers, CSF cytology, or other reliable measures.

12.6.3 Selection of Target and Non-Target Lesions

For most CNS tumors, only one lesion/mass is present and therefore is considered a “target” for measurement/follow up to assess for tumor progression/response. If multiple measurable lesions are present, up to 5 should be selected as “target” lesions. Target lesions should be selected on the basis of size and suitability for accurate repeated measurements. All other lesions will be followed as non-target lesions. The lower size limit of the target lesion(s) should be at least twice the thickness of the slices showing the tumor to decrease the partial volume effect (e.g., 8 mm lesion for a 4 mm slice).

Any change in size of non-target lesions should be noted, though does not need to be measured.

12.6.4 Response Criteria for Target Lesions

Response criteria are assessed based on the product of the longest diameter and its longest perpendicular diameter. Development of new disease or progression in any established lesions is considered progressive disease, regardless of response in other lesions – e.g., when multiple lesions show opposite responses, the progressive disease takes precedence. Response Criteria for target lesions:

- **Complete Response (CR):** Disappearance of all target lesions.
- **Partial response (PR):** $\geq 50\%$ decrease in the sum of the products of the two perpendicular diameters of all target lesions (up to 5), taking as reference the initial baseline measurements.
- **Stable Disease (SD):** Neither sufficient decrease in the sum of the products of the two perpendicular diameters of all target lesions to qualify for PR, nor sufficient increase in a single target lesion to qualify for PD.
- **Progressive Disease (PD):** 25% or more increase in the sum of the products of the perpendicular diameters of the target lesions, taking as reference the smallest sum of the products observed since the start of treatment, or the appearance of one or more new lesions.

12.6.5 Response Criteria for Non-Target Lesions:

- **Complete Response (CR):** Disappearance of all non-target lesions.
- **Incomplete Response/Stable Disease (IR/SD):** The persistence of one or more non-target lesions.
- **Progressive Disease (PD):** The appearance of one or more new lesions and/or unequivocal progression of existing non-target lesions.

12.6.6 Response criteria for tumor markers (if available):

Tumor markers will be classified simply as being at normal levels or at abnormally high levels.

12.6.7 Overall Response Assessment

The overall response assessment takes into account response in both target and non-target lesions, the appearance of new lesions and normalization of markers (where applicable), according to the criteria described in the table below. The overall response assessment is shown in the last column, and depends on the assessments of target, non-target, marker and new lesions in the preceding columns.

Target Lesions	Non-target Lesions	Markers	New Lesions	Overall Response
CR	CR	Normal	No	CR
CR	IR/SD	Normal	No	PR
CR	CR, IR/SD	Abnormal	No	PR
PR	CR, IR/SD	Any	No	PR
SD	CR, IR/SD	Any	No	SD
PD	Any	Any	Yes or No	PD
Any	PD	Any	Yes or No	PD
Any	Any	Any	Yes	PD

Each patient will be classified according to his “best response” for the purposes of analysis of treatment effect. Best response is determined as outlined in Section 12.7 from a sequence of overall response assessments.

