4.2.2 Concomitant Medications

4.2.2.1 Corticosteroids: Patients receiving corticosteroids who have not been on a stable or decreasing dose of corticosteroid for at least 7 days prior to enrollment are not eligible.

4.2.2.2 Investigational Drugs: Patients who are currently receiving another investigational drug are not eligible.

THIS PROTOCOL IS FOR RESEARCH PURPOSES ONLY, SEE PAGE 1 FOR USAGE POLICY

4.2.2.3 Anti-cancer Agents: Patients who are currently receiving other anti-cancer agents are not eligible.

4.2.2.4 Anti-GVHD agents post-transplant:

Patients who are receiving cyclosporine, tacrolimus or other agents to prevent graft-versus-host disease post bone marrow transplant are not eligible for this trial.

4.2.2.5 Anti-inflammatory agents: Patients who are chronically receiving aspirin, ibuprofen or other non-steroidal anti-inflammatory drugs are not eligible.

4.2.2.6 Anti-platelet agents: Patients who are currently receiving anti-platelet agents are not eligible.

4.2.2.7 Anti-hypertensives:

Patients who are receiving anti-hypertensive medications for control of blood pressure at the time of enrollment are not eligible for this trial.

4.2.2.8 Anti-coagulation: Patients who are currently receiving therapeutic anti-coagulation with heparin, low-molecular weight heparin or coumadin are not eligible for this trial.

4.2.2.9 Belimumab: Patients who are currently receiving belimumab (a monoclonal antibody for systemic lupus erythematosus) are not eligible.

4.2.2.10 Bisphosphonate derivatives: Patients who are currently receiving bisphosphonate derivatives are not eligible.

4.2.3 Surgery: Patients who have had or are planning to have the following invasive procedures are not eligible:

- Major surgical procedure, laparoscopic procedure, open biopsy or significant traumatic injury within 28 days prior to enrollment.
- Central line placement or subcutaneous port placement is not considered major surgery. External central lines must be placed at least 3 days prior to enrollment and subcutaneous ports must be placed at least 7 days prior to enrollment
- Core biopsy within 7 days prior to enrollment.
- Fine needle aspirate within 7 days prior to enrollment.
- Surgical or other wounds must be adequately healed prior to enrollment

NOTE: For purposes of this study, bone marrow aspirate and biopsy are not considered surgical procedures and therefore are permitted within 14 days prior to start of protocol therapy.

4.2.4 Bleeding and Thrombosis:

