- Patients with evidence of active bleeding: intratumoral hemorrhage by current imaging, or bleeding diathesis are not eligible.
- Patients with known or prior history in prior 3 months of esophageal varices are not eligible.

THIS PROTOCOL IS FOR RESEARCH PURPOSES ONLY, SEE PAGE 1 FOR USAGE POLICY

- Patients with a history of CNS arterial/ venous thromboembolic events including transient ischemic attack (TIA) or cerebrovascular accident (CVA) within 6 months prior to study enrollment are not eligible.
- Patients with a history of deep vein thrombosis (including pulmonary embolism) within 3 months prior to study enrollment are not eligible.
- Patients with a history of hemoptysis or other signs of pulmonary hemorrhage within 3 months prior to study enrollment are not eligible.
- Patients with a history of \geq Grade 3 bleeding disorders, vasculitis, or had a significant (\geq Grade 3) episode from gastrointestinal bleeding, within 6 months prior to enrollment are not eligible.
- For Part B: Patients with CNS tumors and evidence of new CNS hemorrhage of more than punctate size and/or more than three foci of punctate hemorrhage on baseline MRI obtained within 14 days prior to study enrollment are not eligible. Note: ECHO Gradient MRI sequences per institutional guidelines are required for patients with CNS tumors

- 4.2.5 Patients with known cardiac disease per the New York Heart Association definition such as myocardial infarction, severe or unstable angina, peripheral vascular disease, or congestive heart failure or peripheral vascular disease are not eligible.
- 4.2.6 Patients who have a history of fistula, gastrointestinal ulcer or perforation, or intra-abdominal abscess within 3 months of study enrollment are not eligible.
- 4.2.7 Patients with a history of hypertensive crisis or hypertensive encephalopathy within 6 months of study enrollment are not eligible.
- 4.2.8 Patients who have non-healing wound, unhealed or incompletely healed fracture, or a compound (open) bone fracture at the time of enrollment are not eligible.
- 4.2.9 Immunocompromised patients (other than that related to the primary oncologic diagnosis or to the use of corticosteroids) including patients known to be HIV positive are not eligible.
- 4.2.10 Infection: Patients who have an uncontrolled infection are not eligible.
- 4.2.11 Patients who have received a prior solid organ transplantation are not eligible.

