6.3 Dose Modifications for Infusion-Related Reactions

For patients who have allergic or acute infusion reactions to ramucirumab, therapy modifications based on grade should be as follows.

[figure not shown]
Grade Infusion Related Reaction	Action
Grade 1 Transient flushing or rash, drug fever $< 38^{\circ}\text{C}$	
Monitor patient until recovery from symptoms; infusion rate may be slowed.If the infusion is interrupted, then restart the infusion at 50% of the original infusion rate when symptoms resolve. Monitor patient closely. 
The following prophylactic premedications are recommended: diphenhydramine 1 mg/kg with max 50 mg (or equivalent) and/or acetaminophen 10-15 mg/kg (max 1000 mg) at least 30 minutes before additional ramucirumab administrations, slowing infusion rate as above.

Grade 2 Rash, flushing, urticaria, dyspnea, drug fever $\geq 38^{\circ}\text{C}$	
Stop infusion, begin an IV infusion of normal saline, and treat the subject with diphenhydramine 1 mg/kg with max 50 mg IV (or equivalent) and/or acetaminophen 10-15 mg/kg (max 1000 mg); remain at bedside and monitor patient until resolution of symptoms. Corticosteroid or bronchodilator therapy may also be administered as appropriate.If the infusion is interrupted, then restart the infusion at 50% of the original infusion rate when symptoms resolve. Monitor patient closely.If symptoms recur, then no further ramucirumab will be administered at that visit. Administer diphenhydramine 1 mg/kg with max 50 mg IV (or equivalent), and remain at bedside and monitor the patient until resolution of symptoms. 
The following prophylactic premedications are recommended: diphenhydramine 1 mg/kg with max 50 mg IV (or equivalent) and acetaminophen (10-15 mg/kg, max 1000 mg) should be administered at least 30 minutes before additional ramucirumab administrations. If clinically indicated, corticosteroids (recommended dose: 1-2 mg/kg/day methylprednisolone IV or equivalent) may be used.

Grade 3 or 4 Symptomatic bronchospasm with	
Immediately discontinue infusion of ramucirumab.Begin an IV infusion of normal saline, and treat the subject as follows. Recommend bronchodilators, epinephrine 0.2 to

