### 6.4. Concomitant Therapy

The following concomitant medications will be summarized and listed for the safety population:

- Anticoagulation: Use of therapeutic anticoagulation with heparin, low-molecular weight heparin, or Coumadin should be avoided.
- Anti-platelet agents: Use of aspirin, ibuprofen or other non-steroidal anti-inflammatory drugs or anti-platelet agents for chronic use is not allowed while on study therapy.
- Anti-hypertensives: Patients who develop hypertension while on study therapy may be treated with anti-hypertensive agents and may remain on therapy as long as hypertension is well controlled on medication.

The use of belimumab (a monoclonal antibody for systemic lupus erythematosus) and bisphosphonate derivatives are prohibited while the patient is on study therapy.

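### CNS response is classified without regard to corticosteroid dose, so a sustained steroid-related shrinkage in Part B would count as a ramucirumab response

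*Protocol*

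**What the plan says.** **CNS response.** Protocol 12.6.7: "The overall response assessment takes into account response in both target and non-target lesions, the appearance of new lesions and normalization of markers". Under 12.6.4, a target-lesion PR is a fall of at least 50% from baseline in the sum of the products of the perpendicular diameters. Section 12.7 then derives best response from the sequence of assessments.

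**Steroids at entry.** Protocol 4.2.2.1 concerns patients on corticosteroids; those who "have not been on a stable or decreasing dose of corticosteroid for at least 7 days prior to enrollment are not eligible". Being on steroids does not itself exclude a patient. The exclusion of immunocompromised patients (4.2.9) covers causes "other than that related to the primary oncologic diagnosis or to the use of corticosteroids".

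**Steroids on study.** Protocol 7.1, 7.3 and 7.6 neither name nor restrict corticosteroids. Section 6.3 allows them for a Grade 2 infusion reaction: "Corticosteroid or bronchodilator therapy may also be administered as appropriate". It also permits them with later infusions where clinically indicated.

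**Reporting.** SAP 6.4 begins "The following concomitant medications will be summarized and listed for the safety population" and then names anticoagulants, anti-platelet agents and anti-hypertensives. Corticosteroids are not among them. The schedule of studies in Protocol 8.1 has no steroid-dose item.

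**Role of the endpoint.** Antitumor activity is the secondary aim (Protocol 1.2.1), and its analysis is descriptive (11.5).

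**The concern.** If corticosteroids can reduce the measured size of a CNS lesion, a scan taken on a higher dose than the baseline scan does not isolate the effect of ramucirumab. Part B is a small single-arm cohort with no comparator to absorb the difference. The response definition has no step that asks about dose, and no planned output places the dose next to the response. A reader of the final report could not tell from the planned tables whether a CNS response coincided with a steroid increase. What is at stake is the preliminary activity signal in CNS tumors: response rate, disease control rate, and duration of response.

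**Working it through.** No figure in the plan is disputed. The check is mainly of the text, with arithmetic for scale.

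**1. Can a scan on a raised dose score PR?** In 12.6.7 the overall response "depends on the assessments of target, non-target, marker and new lesions in the preceding columns". Take a target PR, non-target CR or IR/SD, any marker result and no new lesion. The table returns PR, with no condition on steroid dose. If both diameters shrink by the same fraction s, the PR threshold is (1 − s)² = 0.5, so s = 1 − √0.5 = 29.3%. The effect must therefore be large.

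**2. Does the entry rule protect the baseline scan?** Protocol 4.2.4 allows the Part B baseline MRI up to 14 days before enrollment. Section 4.0 requires imaging within 14 days before therapy starts, and 3.9 allows therapy to start up to 5 days after enrollment. The baseline scan can therefore be 14 days old at enrollment if therapy starts the same day, or 14 − 5 = 9 days old if therapy starts on day 5. The steroid rule covers only the last 7 days. The uncovered stretch is 14 − 7 = 7 days at most, or 9 − 7 = 2 days when the start is latest. Example: scan on day −14, dose raised on day −8 and stable afterwards, enrollment and first infusion on day 0. This patient meets the steroid and imaging rules with a baseline scan taken on the lower dose, with no on-study increase.

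**3. Does a later step catch it?**
- *Confirmation.* Protocol 8.1 (footnote 6) calls for re-evaluation at the next cycle after a first PR or CR. In 12.7 Table 3, PR requires PR followed by PR or CR. Stable followed by PR stays Stable, and PR with no second assessment is unclassifiable. A brief effect fails; one that persists while the dose stays up passes.
- *Central review (8.3.2).* It is described as a review of images, with no mention of dose.
- *SAP 6.5.1.* It scores ORR by RECIST 1.1, again with no steroid condition.

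**4. How large is one such response?** Enrollment figures in Protocol 11.1 reproduce: 6/(1 − 0.20) = 7.5, rounded up to 8; 12/0.80 = 15. SAP 6.5.1 uses treated patients as the denominator and counts unassessed patients as nonresponders. If all those enrolled are treated:

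| Part B treated | No response (exact 95% CI) | One response (exact 95% CI) |
|---|---|---|
| 8 | 0% (0 to 36.9%) | 12.5% (0.3 to 52.7%) |
| 15 | 0% (0 to 21.8%) | 6.7% (0.2 to 31.9%) |

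SAP 6.5.2 reports ORR by dose level and does not specify a separate Part B rate. Pooled with the 12 evaluable Part A patients planned at the RP2D (Protocol 11.2.3), one response is 1/(8 + 12) = 5.0% or 1/(15 + 12) = 3.7%.

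**5. How often?** The documents give no rate. For an assumed per-patient chance q of a confirmed steroid-driven PR, the chance of at least one among n patients is 1 − (1 − q)ⁿ:

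| q (assumed) | n = 8 | n = 15 |
|---|---|---|
| 1% | 7.7% | 14.0% |
| 5% | 33.7% | 53.7% |
| 10% | 57.0% | 79.4% |
| 20% | 83.2% | 96.5% |

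The size threshold and the confirmation rule argue for the lower rows, but nothing in the documents fixes q.

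**The case against.** The case for leaving the plan alone has real weight.

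- **Any shrinkage after a steroid increase is scored as response.** A reader might infer this, and it goes too far. The fall must reach 50%, and it must hold at a second evaluation.
- **On-study exposure.** The only explicit permission is for infusion reactions, which Protocol 9.1.8 lists as rare (3% or less). The last infusion of a cycle is on Day 29 and the evaluation on Day 42. Wider use is inferred from silence, and no section addresses raising steroids for CNS symptoms. Clinical progression also removes a patient from therapy (10.1), perhaps before a confirmatory scan. These points make the event less likely. They do not close the gap, and the baseline-scan route needs no on-study increase.
- **The confounding could not be seen afterwards.** This is also tempting, but the documents show only that no steroid summary is prespecified. The case report forms are a separate packet (14.1), SAP 6.1 has date rules for concomitant therapy, and SAP 6 allows further exploratory analyses.
- **Larger percentages.** Using evaluable patients gives 1/6 = 16.7% or 1/12 = 8.3%, but the SAP's denominator is treated patients.
- **The bias is always upward.** It is not. A steroid increase matters to ORR only if it carries a confirmed response over the threshold, and growth after a reduction could be scored PD.

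It also stands that no dose or safety decision uses CNS response.

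**Conclusion.** The gap is real and is not repaired elsewhere in the protocol or SAP: a fall of at least 50% that is due to steroids and persists through confirmation would be credited to ramucirumab. One such response would add 12.5 percentage points to a Part B response rate on 8 treated patients, or 6.7 on 15, and less if the rate is pooled by dose level. This rests on two assumptions from outside the documents: that corticosteroids can shrink CNS lesions on MRI, and that this happens at some unknown frequency. The endpoint is secondary and descriptive, and the DLT and RP2D decisions are unaffected. The point is a worthwhile, inexpensive improvement to response classification and reporting; it does not threaten the trial's primary conclusions.

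**What to change.** 1. Record the corticosteroid dose at the baseline MRI and at each CNS disease evaluation.
2. State in Protocol 12.6.7 that CR or PR, including at the confirmatory scan, counts only if the corticosteroid dose is no higher than at the baseline MRI. Otherwise the scan scores SD at best, with the PD rules unchanged.
3. Put the same rule in SAP 6.5.1 for CNS patients. Without it, the ORR defined there would not change.
4. Add corticosteroids to SAP 6.4 and list the dose beside each CNS response, so that affected CR, PR, SD and PD calls are all visible. The listing matters because the SD cap does not address progression masked by a higher dose or growth after a reduction.

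The cost is one data field, one sentence in each document and one listing. The downside is that a few true responses may be downgraded after a minor or passing dose increase; the listing lets a reader see which ones. If Part B data already exist, the listing alone would show whether any claimed response is affected. The change concerns classification and reporting only, not how steroids are used clinically.

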12.7 Best Response**12.7.1 Evaluation of Best Overall Response**

The best overall response is the best response recorded from the start of the treatment until disease progression/recurrence (taking as reference for progressive disease the smallest measurements recorded since the treatment started). The patient's best response assignment will depend on the achievement of both measurement and confirmation criteria.

Table 1: For Patients with Measurable Disease (i.e., Target Disease)

Target	Non-Target	New	Overall	Best Overall Response
--------	------------	-----	---------	-----------------------

THIS PROTOCOL IS FOR RESEARCH PURPOSES ONLY, SEE PAGE 1 FOR USAGE POLICY

Lesions	Lesions	Lesions	Response	when Confirmation is Required*
CR	CR	No	CR	≥ 28 days Confirmation
CR	Non-CR/Non-PD	No	PR	≥ 28 days Confirmation
CR	Not evaluated	No	PR	
PR	Non-CR/Non-PD/not evaluated	No	PR	
SD	Non-CR/Non-PD/not evaluated	No	SD	documented at least once ≥ 28 days from baseline
PD	Any	Yes or No	PD	no prior SD, PR or CR
Any	PD**	Yes or No	PD	
Any	Any	Yes	PD	

* See RECIST 1.1 manuscript for further details on what is evidence of a new lesion.
** In exceptional circumstances, unequivocal progression in non-target lesions may be accepted as disease progression.

Note: Patients with a global deterioration of health status requiring discontinuation of treatment without objective evidence of disease progression at that time should be reported as "symptomatic deterioration." Every effort should be made to document the objective progression even after discontinuation of treatment.

Table 2: For Patients with Non-Measurable Disease (i.e., Non-Target Disease)

Non-Target Lesions	New Lesions	Overall Response
CR	No	CR
Non-CR/non-PD	No	Non-CR/non-PD*
Not all evaluated	No	not evaluated
Unequivocal PD	Yes or No	PD
Any	Yes	PD

* 'Non-CR/non-PD' is preferred over 'stable disease' for non-target disease since SD is increasingly used as an endpoint for assessment of efficacy in some trials so to assign this category when no lesions can be measured is not advised

Table 3. Sequences of overall response assessments with corresponding best response.

1 st Assessment	2 nd Assessment	Best Response
Progression		Progressive disease
Stable, PR, CR	Progression	Progressive disease
Stable	Stable	Stable
Stable	PR, CR	Stable
Stable	Not done	Not RECIST classifiable
PR	PR	PR
PR	CR	PR
PR, CR	Not done	Not RECIST classifiable
CR	CR	CR

Table 4: Overall Response for Patients with Neuroblastoma and Measurable Disease

CT/MRI	MIBG	Bone Scan	Bone Marrow	Catechol	Overall
PD	Any	Any	Any	Any	PD

Any	PD	Any	Any	Any	PD
Any	Any	PD	Any	Any	PD
Any	Any	Any	PD	Any	PD
SD	CR/PR/SD	Non-PD	Non-PD	Any	SD
PR	CR/PR	Non-PD	Non-PD	Any	PR
CR/PR	PR	Non-PD	Non-PD	Any	PR
CR	CR	Non-PD	Non-PD	Elevated	PR
CR	CR	CR	CR	Normal	CR

Table 5: Overall Response Evaluation for Neuroblastoma Patients and MIBG Positive Disease Only

If patients are enrolled without disease measurable by CT/MRI, any new or newly identified lesion by CT/MRI that occurs during therapy would be considered progressive disease.

MIBG	CT/MRI	Bone Scan	Bone Marrow	Catechol	Overall
PD	Any	Any	Any	Any	PD
Any	New Lesion	Any	Any	Any	PD
Any	Any	PD	Any	Any	PD
Any	Any	Any	PD	Any	PD
SD	No New Lesion	Non-PD	Non-PD	Any	SD
PR	No New Lesion	Non-PD	Non-PD	Any	PR
CR	No New Lesion	Non-PD	Non-PD	Elevated	PR
CR	No New Lesion	CR	CR	Normal	CR

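### Two rows of Table 3 in Protocol 12.7.1 contradict Table 1 and the section's own definition of best overall response; SAP 6.5.2 avoids both errors but omits the 28-day and confirmation rules

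*Protocol*

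**What the plan says.** Protocol 12.7.1 opens with a definition: "The best overall response is the best response recorded from the start of the treatment until disease progression/recurrence". It adds that the "best response assignment will depend on the achievement of both measurement and confirmation criteria".

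Table 1, for measurable disease, puts these ideas into rules. CR and PR need confirmation at 28 days or more. SD must be "documented at least once ≥ 28 days from baseline". PD as best response carries the condition "no prior SD, PR or CR".

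Table 3 maps a first and a second assessment to a best response. Two of its rows matter here (first assessment, second assessment, best response):

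- "Stable, PR, CR Progression Progressive disease"
- "Stable Not done Not RECIST classifiable"

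Protocol 12.2.5, 12.3.6, 12.5.2 and 12.6.7 all send the reader to Section 12.7 to derive best response from the series of assessments. Table 3's title describes almost exactly that task. Protocol 12.7.2 measures stable disease from the start of treatment until progression.

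SAP 6.5.2 gives its own one-sentence rule: the best result up to progression, ranked CR, PR, SD. It cites neither Section 12.7 nor Table 3. SAP 6.5.1 builds the objective response rate (ORR) and DCR on best overall response, with treated patients as the denominator.

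**The concern.** A patient who is stable at the end of Cycle 1 and progresses at the end of Cycle 2 has best response SD by the section's definition and by Table 1, but PD by Table 3. A patient who is stable at the end of Cycle 1 and has no further scan is SD by Table 1 and unclassifiable by Table 3. The protocol does not rank the tables, and its cross-references lead naturally to Table 3.

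At stake are the best-overall-response categories reported by dose level (Protocol 11.6.7) and any DCR derived from them. If the duration-of-stable-disease summary is limited to patients whose best response is SD, its membership is affected too. Leaving the choice of table open until the scans are in would also allow it to be made with the outcomes known.

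**Working it through.** The documents give no response figure to reproduce, so the check applies each rule to the planned scan schedule.

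**Inputs**

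- Cycle length 42 days, disease evaluation on Day 42 (Protocol 5.1).
- Scans at the end of Cycles 1 and 2, then every other cycle (design schema; Section 8.1).
- Baseline imaging 0 to 14 days before the start of therapy (Protocol 4.0).
- SD minimum of 28 days from baseline (Protocol 12.7.1, Table 1).
- DCR denominator: treated patients (SAP 6.5.1).
- Group sizes: 6 (one cohort, or Part B), 12 (total at the expanded dose), 24 (planned evaluable maximum in Part A).

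**Step 1. Does an on-schedule first scan meet the 28-day rule?**

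- Shortest interval, baseline scan on Day 1: 42 − 1 = 41 days (42 if Day 42 is counted as 42 days after the start).
- Longest interval, baseline scan 14 days earlier: 41 + 14 = 55 days (or 56).
- Section 8.1 allows studies up to 72 hours before the next cycle. Taking three days off the shortest interval leaves 41 − 3 = 38 days.

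All exceed 28. A short interval therefore cannot explain why Table 3 treats SD followed by no scan as unclassifiable.

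**Step 2. The rules side by side**

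| First scan, second scan | Table 1 and section text | Table 3 | SAP 6.5.2 read literally |
|---|---|---|---|
| SD, PD | SD | **PD** | SD |
| SD, none | SD | **Not classifiable** | SD |
| PR or CR, PD | Not PD; response unconfirmed, no category named | **PD** | PR or CR |
| PR or CR, none | Response unconfirmed, no category named | Not classifiable | PR or CR |
| SD, then PR or CR | SD (response not yet confirmed) | SD | PR or CR |
| SD, SD | SD | SD | SD |
| PR, PR | PR | PR | PR |
| PR, CR | PR | PR | CR |
| CR, CR | CR | CR | CR |

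The bold cells contradict Table 1; they come from the two rows quoted above. The SAP column agrees with Table 1 on both SD sequences, but parts from the protocol wherever a response lacks confirmation.

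**Step 3. Size per patient**

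Each SD patient coded from Table 3 as PD or unclassifiable lowers DCR by 100 × 1/N points:

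- N=6: 100/6 = 16.7
- N=12: 100/12 = 8.3
- N=24: 100/24 = 4.2

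Likewise, each unconfirmed PR or CR counted under the SAP but not under the protocol moves ORR by 1/N.

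The number of such patients is not in the documents. If a share *s* of treated patients followed either SD sequence, the expected DCR gap would be 100 × *s* points: 10, 20 or 30 points for assumed shares of 10%, 20% or 30%. The probability of at least one affected patient among 12 is 1 − (1 − *s*)^12, which is 72%, 93% or 99%. These shares are assumptions, not estimates.

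**The case against.** The strongest reply is that the planned analysis is already protected. DCR appears only in the SAP, and SAP 6.5.2 supplies its own rule, which gives SD for both SD sequences. On SD followed by progression, the lead sentence, Table 1, 12.7.2 and the SAP all agree, so Table 3 is the lone outlier and the intent is plain. This stands, and it limits the point: DCR changes only if someone codes best response from Table 3. It does not remove the contradiction, because the protocol's cross-references lead to Section 12.7 and nothing there subordinates Table 3. Nor does the SAP sentence carry the 28-day and confirmation rules, so an analyst still has to return to 12.7.1 for them.

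A reader might infer more than the documents support:

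- **That the row "PR, CR Not done Not RECIST classifiable" also contradicts Table 1.** Table 1 requires confirmation and names no category for a response that lacks it. This is a gap, not a conflict. Nor does the row "Stable PR, CR Stable" show that an unconfirmed response becomes SD, since its first assessment is itself stable.
- **That a PR first seen at the second scan and confirmed at the third would be lost because Table 3 stops at two assessments.** The lead sentence runs until progression and Protocol 12.2 requires a confirmatory scan. Losing that response would mean ignoring both.
- **That the adult progression-free survival medians in Protocol 2.3 tell us how many patients would be misclassified.** Those trials enrolled adults with other tumors. Medians alone also do not separate SD from response, or imaging progression from death. They do not measure the effect here.

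**Conclusion.** The concern holds in a limited form. Two Table 3 rows are wrong by the protocol's own definition and by Table 1, and no precedence rule rescues them. Best overall response coded from Table 3 would be misclassified, at a cost to DCR of 8.3 points per affected SD patient at N=12 (16.7 at N=6). The conclusion on SD followed by no scan assumes that the first scan is on schedule; the per-patient sizes assume that the number treated equals the N shown.

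The documents do not support saying that DCR under SAP 6.5.2 is wrong: that rule gives SD for both sequences. The SAP's own defect is separate. It omits the 28-day SD minimum and the confirmation of CR and PR, so ORR read literally from the SAP can include responses that the protocol would not count.

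Antitumor activity is a secondary aim analyzed descriptively (Protocol 1.2 and 11.5). MTD and RP2D are unaffected. This is a correction worth making before analysis, not a threat to the trial's main conclusions.

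**What to change.** **Protocol 12.7.1, Table 3.** Correct or delete the two rows, so that SD documented at 28 days or more from baseline stays SD when progression or no scan follows, and PR or CR followed by progression is not classed as PD. Table 1 does not say which category an unconfirmed response takes instead, so that choice is the authors' to make and state.

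**Protocol 12.7.1, one note.** State that for measurable disease Table 1 and the section text prevail, and that Table 3 illustrates only the first two assessments. The limit to measurable disease is needed because Table 1 is headed that way, and Table 2's footnote advises against assigning SD where no lesion can be measured.

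**SAP 6.5.2, one sentence.** State that best overall response follows Protocol 12.7.1 as corrected, including the 28-day SD minimum and confirmation of CR and PR at 28 days or more.

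**Cost.** Two table rows, one note and one SAP sentence. No extra imaging is needed, since Protocol 12.2 and Section 8.1 (footnote 6) already call for a confirmatory scan in the next cycle. The downside is that ORR may come out slightly lower once confirmation is required.
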